10.3 Computation Formula for Derived HHD Variables

Individual Muscle Strength Average Score = (left-side measurement + right-side measurement) / 2

UE Composite Score = sum(Individual Muscle Strength Average Score for muscle group gross grip, shoulder abductors, elbow flexors and elbow extensors)

LE Composite Score = sum(Individual Muscle Strength Average Score for muscle group knee flexors, hip flexors, hip extensors, hip abductors and hip adductors)

Predicted Normal for Individual Muscle Strength Average Score = (left-side predicted normal + right-side predicted normal) / 2

Predicted Normal for UE Composite Score = sum(Predicted Normal for Individual Muscle Strength Average Score for muscle group gross grip, shoulder abductors, elbow flexors and elbow extensors)

Predicted Normal for LE Composite Score = sum(Predicted Normal for Individual Muscle Strength Average Score for muscle group hip flexors, hip extensors, hip adductors and knee flexors)

% of predicted normal HHD values = (Observed strength value/ Predicted normal strength value) *100%.

Predicted normal HHD values can be derived using the regression equations outlined in Appendix 10.3.1.

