#### ***Phase 2 Efficacy and Safety Extension Study (UX001-CL202):***

In addition to the study data from UX001-CL201, the UX001-CL202 study allowed for the continuation of open-label treatment with 6 g/day of Ace-ER in the original 46 subjects who crossed over to UX001-CL202. In addition, 13 subjects who were naïve to Ace-ER and who could walk  $\geq$  200 m in the 6MWT were enrolled.

In the UX001-CL202 extension study, after approximately 2.5 years of treatment over the course of two studies in subjects with a progressive, debilitating disease, muscle strength remained stable in 7 of 9 of the individual muscle groups comprising the upper extremity composite (UEC) and the LEC muscle strength scores in the combined 0/6 and 6/6 group. Grip strength and hip abductors decreased modestly from original study baseline, resulting in decreases in overall UEC and LEC muscle strength scores.

For both the upper and lower extremities, subjects treated with 6 g/day at the beginning of the 201 study had the greatest strength at the end of approximately 2.5 years compared to patients who started 6g at Week 24 or received 3 g/day at any time during the first year.

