#### 7.5.2.1.1 Upper Extremity Composite Score

**For UX001-CL202 and UX001-CL301 Subjects:** Muscle strength based on the MVIC against a dynamometer will be measured bilaterally in the following upper extremity muscle groups: gross grip, shoulder abductors, elbow flexors, and elbow extensors. The UEC is derived from the sum of the average of the right and left total force values (measured in kg) for each muscle group.

The percent predicted total force values will be determined based on reference equations adjusting for age, gender, height, and weight. The percent predicted force will be calculated for each side and the bilateral percent predicted values will be averaged for each upper extremity muscle group (gross grip, shoulder abductors, elbow flexors, and elbow extensors). The mean of the four averages in percent predicted scores will be calculated to create a percent predicted UEC score, and analyzed relative to baseline to create a UEC mean change in percent predicted score.

**For UX001-CL203 Subjects:** Muscle strength based on the MVIC against a dynamometer will be measured bilaterally in the following upper extremity muscle groups: grip, key pinch, shoulder abductors and wrist extensors. The UEC is derived from the sum of the average of the right and left total force values (measured in kg) for each muscle group.

The percent predicted total force values will be determined based on reference equations adjusting for age, gender, height, and weight. The percent predicted force will be calculated for each side and the bilateral percent predicted values will be averaged for each upper

extremity muscle group (grip, key pinch, shoulder abductors and wrist extensors). The mean of the four averages in percent predicted scores will be calculated to create a percent predicted UEC score, and analyzed relative to baseline to create a UEC mean change in percent predicted score.

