#### **7.5.2.1.2 Lower Extremity Composite Score**

**For UX001-CL202 and UX001-CL301 Subjects:** muscle strength based on MVIC against a dynamometer will be measured bilaterally in the following lower extremity muscle groups: knee flexors, hip flexors, hip extensors, hip abductors and hip adductors. The LEC is derived from the sum of all muscle groups. Each muscle group is the average of the right and left total values (measured in kg).

The percent predicted total force values for the LEC will also be determined and analyzed as a tertiary endpoint. The percent predicted force will be calculated for each side and the bilateral percent predicted values will be averaged for each lower extremity muscle group (knee flexors, hip flexors, hip extensors, hip abductors and hip adductors). The mean of the five averages in percent predicted scores will be calculated to create a percent predicted LEC score, and analyzed relative to baseline to create a LEC mean change in percent predicted score.

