Left Elbow Extension	$-(\text{age} * 0.07) + (\text{gender} * 8.18) + ((\text{weight}/\text{height}^2) * 0.17) + 11.32$
Right Hip Flexion	$-(\text{age} * 0.33) + (\text{gender} * 19.19) + ((\text{weight}/\text{height}^2) * 0.66) + 34.44$
Left Hip Flexion	$-(\text{age} * 0.29) + (\text{gender} * 18.75) + ((\text{weight}/\text{height}^2) * 0.47) + 36.05$
Right Hip Extension	$-(\text{age} * 0.21) + (\text{gender} * 15.19) + ((\text{weight}/\text{height}^2) * 0.14) + 33.52$
Left Hip Extension	$-(\text{age} * 0.23) + (\text{gender} * 15.02) + ((\text{weight}/\text{height}^2) * 0.17) + 33.88$
Right Knee Flexion	$-(\text{age} * 0.16) + (\text{gender} * 8.78) + ((\text{weight}/\text{height}^2) * 0.08) + 22.47$
Left Knee Flexion	$-(\text{age} * 0.17) + (\text{gender} * 7.67) + ((\text{weight}/\text{height}^2) * 0.14) + 21.10$
Right Knee Extension	$-(\text{age} * 0.38) + (\text{gender} * 18.44) + ((\text{weight}/\text{height}^2) * 0.62) + 34.41$
Left Knee Extension	$-(\text{age} * 0.38) + (\text{gender} * 17.68) + ((\text{weight}/\text{height}^2) * 0.62) + 33.61$

(NIMS 1996)

Strength prediction results in kilograms (kg)

Age = years; gender: male = 1, female = 0; weight = kg;; height = meters

Note: Age, height and weight values collected at the Baseline visit will be used for the calculation of predicted values for elbow flexion, elbow extension, hip flexion, hip extension, knee flexion and knee extension for all study time points.

Gross Grip

Normative grip strength values for the Jamar dynamometer for clinical use (in pounds)

Age (years)	Females (n = 355)			Males (n = 365)		
	Number of subjects	5 th %ile Jamar values (lbs)	Median Jamar values (lbs)	Number of subjects	5 th %ile Jamar values (lbs)	Median Jamar values (lbs)
20 - 29	51	50	62	50	81	100
30 – 39	50	49	64	51	80	105
40 – 49	50	48	63	50	78	107
50 – 59	51	45	61	54	73	104
60 – 69	49	40	56	58	64	95
70 - 79	50	32	46	50	51	77
≥ 80	54	22	34	52	34	54

(Peters et al. 2011)

Note: The age category that applies for a subject at the Baseline visit will be used for the calculation of predicted grip values for all study time points.

Walking Ability

Calculation of Predicted Six-Minute Walk Test Distance

6MWT Distance (meters) = 868.8 - (2.99*Age) - (74.7*Gender)

Age in years. Men = 0 and Women = 1.

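### UEC and LEC percent predicted (tertiary endpoint): SAP 10.3 implies a ratio of sums where the protocol takes a mean of percentages, and its LEC denominator leaves out hip abductors

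*SAP*

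**What the plan says.** Protocol 7.5.2.1.1 works upward from the single measurement: percent predicted for each side, then the average of the two sides for each muscle group, and then "The mean of the four averages in percent predicted scores will be calculated to create a percent predicted UEC score". Section 7.5.2.1.2 does the same for the lower limb: "The mean of the five averages in percent predicted scores will be calculated to create a percent predicted LEC score". The five groups are knee flexors, hip flexors, hip extensors, hip abductors and hip adductors. The protocol synopsis repeats the UEC rule and says that the LEC is handled similarly.

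SAP 10.3 contains no mean of percentages. It defines a predicted normal for each composite as a sum of predicted forces; for the upper limb, "Predicted Normal for UE Composite Score = sum(Predicted Normal for Individual Muscle Strength Average Score for muscle group gross grip, shoulder abductors, elbow flexors and elbow" (the quote breaks off at the fourth group, the elbow extensors). It then gives one general percentage formula, percent "of predicted normal HHD values = (Observed strength value/ Predicted normal strength value) *100". The observed LEC in the same section sums five groups. The predicted LEC sums four: hip flexors, hip extensors, hip adductors and knee flexors.

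SAP 4.2 lists the endpoint as tertiary, and SAP Appendix 10.1 plans summary statistics for it. The SAP introduction gives the SAP precedence over the protocol on analysis methods. The issue does not extend to CL203 subjects, for whom the footnote to SAP Table 4.2.1 says that no UEC is defined.

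**The concern.** A mean of percentages gives every muscle group the same say. A ratio of summed forces weights each group by its normal strength, so grip dominates the UEC and hip flexors dominate the LEC. The same subject can get two different values and two different changes. A reader who knows the protocol definition would misread a table produced under SAP 10.3, because nothing in the SAP says that the definition has moved.

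The ratio also adds less information. Predicted values are fixed at baseline (Protocol 7.5.5.3.1; notes in SAP 10.3.1). Under the SAP rule a subject's UEC percent predicted is therefore the UEC in kg times a constant, and within a subject it repeats the primary efficacy variable.

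For the LEC there is a plain error as well. A five-group numerator over a four-group denominator is not a percentage of normal at all.

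**Working it through.** The documents state no muscle-group weights, so there is no figure of theirs to reproduce. The check has four steps.

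**1. Algebra.** Observed sum / predicted sum = Σ wᵢ × (observedᵢ / predictedᵢ), with wᵢ = predictedᵢ / Σ predicted. Under the protocol wᵢ = 1/4 for the UEC and 1/5 for the LEC.

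**2. UEC weights at age 40.** Inputs are the SAP 10.3.1 equations and the median column of its grip table ("Normative grip strength values for the Jamar dynamometer for clinical use (in pounds"), ages 40-49: 107 lb for men, 63 lb for women. Body size is assumed: man 75 kg and 1.75 m, woman 60 kg and 1.62 m. Conversions: 1 lb = 0.45359 kg, 1 kg = 9.80665 N.

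Example, shoulder abduction in the man (weight 75 × 9.80665 = 735.5 N):
- nondominant: 165.16 − 0.910×40 + 0.126×735.5 = 221.4 N
- dominant: 178.90 − 1.128×40 + 0.134×735.5 = 232.3 N
- mean: 226.9 N = 23.1 kg

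| Predicted, mean of sides | Man, kg | SAP weight | Woman, kg | SAP weight | Protocol weight |
|---|---|---|---|---|---|
| Grip | 48.5 | 0.399 | 28.6 | 0.395 | 0.25 |
| Elbow flexors | 28.8 | 0.24 | 17.8 | 0.25 | 0.25 |
| Shoulder abductors | 23.1 | 0.19 | 13.4 | 0.19 | 0.25 |
| Elbow extensors | 21.1 | 0.17 | 12.6 | 0.17 | 0.25 |
| Sum (unrounded values) | 121.6 | 1 | 72.4 | 1 | 1 |

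Over ages 25-65 and assumed sizes (women 1.62 m, 50-80 kg; men 1.76 m, 60-95 kg) the grip weight runs from 34.8% to 42.7%. The SAP does not say which grip column applies. With the 5th percentile (men 78 lb = 35.4 kg, women 48 lb = 21.8 kg) the weights at age 40 are 35.4/108.5 = 0.33 and 21.8/65.6 = 0.33.

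**3. Effect on the UEC score (man above).**
- Grip falls 10 points, the rest unchanged: protocol 10×0.25 = 2.5 points; SAP 10×0.399 = 4.0 points.
- Shoulder abductors fall 10 points, the rest unchanged: protocol 2.5; SAP 10×0.19 = 1.9.
- All four groups fall 10 points: 10 points under both, since both sets of weights sum to 1.
- A level, for illustration: grip at 40% and the other three at 80% gives (40+80+80+80)/4 = 70.0% under the protocol and (0.4×48.5 + 0.8×73.1)/121.6 = 64.0% under the SAP.

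**4. LEC as SAP 10.3 writes it.** Predicted kg at age 40, same two people:

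| Group | Man | Woman |
|---|---|---|
| Hip flexors | 55.65 | 35.76 |
| Hip extensors | 43.80 | 28.44 |
| Hip adductors | 31.87 | 21.55 |
| Knee flexors | 26.10 | 17.70 |
| Four-group sum (SAP denominator) | 157.4 | 103.5 |
| Hip abductors | 29.99 | 20.14 |
| Five-group sum | 187.4 | 123.6 |

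With every group at the same percentage, the result is too high by 187.4/157.4 = 1.19 (man) or 123.6/103.5 = 1.19 (woman). A subject at 60% in all five groups would be reported at 60×1.19 = 71.4%. A uniform fall of 10 points would be reported as 11.9. Hip flexors get a coefficient of 55.65/157.4 = 0.35 (woman 35.76/103.5 = 0.35) instead of 0.20, and the five coefficients sum to 1.19 instead of 1. Over the ages and sizes in step 2 the inflation is about 1.18 to 1.24.

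**The case against.** Several objections carry weight.

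- *Rank.* The endpoint is tertiary and is to be summarised only. SAP 8.6 speaks generally of GEE for continuous endpoints, but the row for this endpoint in Appendix 10.1 says summary statistics. No decision or sample size rests on it. This stands and limits the importance of the point.
- *Precedence.* The SAP prevails on analysis methods, so one may say there is no live conflict. That settles which text wins if an endpoint derivation counts as an analysis method. It does not tell the reader that the definition has changed, and it does not repair the LEC denominator.
- *Legitimacy.* A ratio of sums is a respectable score. It weights forces as the primary UEC in kg does, and it still standardises for age, sex and size across subjects. This stands: for the UEC, the fault is an undeclared change, not an invalid formula.
- *Inference.* The SAP never writes UEC percent predicted as UEC over predicted UEC on one line. True, but a summed predicted composite has no other evident use in that section.

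A reader might also infer that the SAP formula will exaggerate a known decline, because the protocol reports from CL202 that "Grip strength and hip abductors decreased modestly from original study baseline". The documents do not support this. That sentence concerns strength and strength scores, not percent predicted, and it calls the decrease modest. Force and percent predicted are also reported for each muscle group separately, so a grip decline stays visible under either formula.

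Nor is it right to describe the SAP's LEC as a five-group ratio in which hip flexors weigh 0.29-0.30. That score would need a five-group denominator, which SAP 10.3 does not have.

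**Conclusion.** The concern holds, as a correction to a tertiary endpoint. The protocol and SAP 10.3 define different UEC and LEC percent-predicted scores, and the SAP does not acknowledge the difference.

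For the UEC, the gap matters only when muscle groups change unequally: up to about 1.5 points per 10-point fall in grip alone (4.0 against 2.5) at age 40. The 40% grip weight is not a constant. It rests on the median grip column and on assumed body sizes, and the plausible range is about 35-43%, or about 33% at age 40 with the 5th-percentile column.

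For the LEC, the formula as written is an error under any reading that divides the observed composite by the predicted one. The 1.19-fold inflation is exact only for a subject with equal percentages in all groups; for others it depends on how strong the hip abductors are relative to the rest.

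It would be too strong to conclude that the efficacy results at large are compromised. The primary UEC in kg, the LEC in kg and the safety endpoint do not use these formulas.

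**What to change.** In SAP 10.3, replace the two lines that sum predicted force for the upper and lower composites. Define UEC percent predicted as the mean of the four muscle-group percentages and LEC percent predicted as the mean of the five, each group percentage being the average of the two sides' percentages, as in Protocol 7.5.2.1.1 and 7.5.2.1.2. Apply the same formula to parent-study baseline values wherever SAP Table 8.1.1 calls for that baseline for this endpoint (CL301). This also removes the hip-abductor mismatch. State which grip column supplies the predicted value.

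If the sponsor prefers the ratio of sums, it should write the formula out, declare it as a change from the protocol, and add hip abductors to the predicted LEC sum. The documents do not show which formula the parent studies used, so this should be checked before parent-baseline values are carried over.

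The cost is a few lines of SAP text and derivation code. No new data are needed.

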1 INTRODUCTION

The purpose of this Statistical Analysis Plan (SAP) is to provide details of the statistical analyses that have been outlined within the UX001-CL302 original protocol dated 10 February 2016 and the UX001-CL302 Protocol Amendment 1 dated 17 June 2016. Should there be a difference between the SAP and the protocol with respect to analysis methods, the SAP will take precedence over the protocol.

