4.2 Efficacy Endpoints

Efficacy evaluations will be based on the parent study (UX001-CL202, UX001-CL301, or UX001-CL203) from which the subjects enroll. Subjects enrolling from UX001-CL202 follow the same schedule of visits for the efficacy assessments as subjects who roll over from UX001-CL301. Subjects enrolling from UX001-CL203 follow a different schedule of visits.

For subjects enrolling from UX001-CL202 and UX001-CL301:

Primary Clinical Efficacy Endpoint:

- Changes from baseline in upper extremity composite score (UEC) based on bilateral strength recorded in the following muscle groups: gross grip, shoulder abductors, elbow flexors, and elbow extensors as measured by dynamometry. The UEC is derived from the sum of the average of the right and left total force values (measured in kg);

Secondary Clinical Efficacy Endpoints:

- Changes from baseline in the scores on the mobility domain of GNEM-FAS;
- Change from baseline in the scores on the upper extremity domain of GNEM-FAS;
- Changes from baseline in lower extremity composite score (LEC) based on bilateral strength recorded in the following muscle groups: knee flexors, hip flexors, hip extensors, hip abductors and hip adductors as measured by dynamometry. The LEC is derived from the sum of the average of the right and left total force values;
- Change from baseline in the number of stands in the Sit-to-Stand test;
- Changes from baseline in the number of lifts in 30 second weighted arm lift;
- Changes from baseline in meters walked in 6MWT and percent predicted distance based on normative data for age and gender;
- Changes from baseline in total force and percent predicted total force in the Knee Extensors. The percent predicted total force value will be determined based on reference equations adjusting for age, gender, height, and weight.

Tertiary Efficacy Endpoints:

- Changes from baseline in UEC and LEC percent predicted based on reference equations adjusting for age, gender, height, and weight;
- Changes from baseline in bilateral total force and percent predicted total force for each individual muscle group included in the UEC and LEC;
- Changes from baseline in the score on self-care domain on GNEM-FAS;
- Changes from baseline in the total score on GNEM-FAS;

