10.3.1 Predicted Normal HHD Muscle Strength

Muscle Strength

Note: Many of the HHD derived variables detailed below rely on regression equations that have predictor variables in units different than what is found in the analysis datasets. Care will be taken to convert dataset variables to the correct units before they are entered into the prediction equation. The resulting predicted value will then, in turn, be converted to the appropriate unit for analysis.

Hand-Held Dynamometry

Shoulder abduction and hip abduction

Regression Equations and Multiple Correlations of Sex, Age, and Weight with Muscle Strength

Muscle Action	Side	Equation*	R	R ²
Shoulder Abduction	Nondominant	$165.16 - 74.9S - .910A + .126W$.843	.710
	Dominant	$178.90 - 77.1S - 1.128A + .134W$.843	.710
Hip Abduction	Nondominant	$203.32 - 73.3S - 1.247A + .192W$.794	.630
	Dominant	$195.24 - 62.4S - 1.184A + .198W$.764	.584

(Bohannon 1997b)

*Muscle strength results in Newtons (N). S, sex (male=0, female=1); A, age (years); W, weight (Newtons).

Note: Age and weight values collected at the Baseline visit will be used for the calculation of predicted values for shoulder abduction and hip abduction for all study time points.

Hip adduction

Muscle Action	Gender	Side	Age (years)	Equation
Hip Adduction	Female	Left	≤ 55	$19.1 - 0.30*(age - 55)$
		Right	≤ 55	$19.5 - 0.00*(age - 55)$
	Female	Left	> 55	$19.1 - 0.212*(age - 55)$
		Right	> 55	$19.5 - 0.245*(age - 55)$
Hip Adduction	Male	Left	≤ 49	$31.8 + 0.044*(age - 49)$
		Right	≤ 49	$31.6 - 0.082*(age - 49)$
	Male	Left	> 49	$31.8 - 0.280*(age - 49)$
		Right	> 49	$31.6 - 0.206*(age - 49)$

(Stoll et al. 2000)

Median strength results in kiloponds (kp) also known as kilogram-force (kgf)

Note: The age category that applies for a subject at the Baseline visit will be used for the calculation of hip adduction predicted values for all study time points.

Elbow flexion, elbow extension, hip flexion, hip extension, knee flexion, knee extension

Regression Equations for Strength Prediction

Muscle Action	Equation
Right Elbow Flexion	$-(\text{age} * 0.13) + (\text{gender} * 11.24) + ((\text{weight}/\text{height}^2) * 0.07) + 22.78$
Left Elbow Flexion	$-(\text{age} * 0.11) + (\text{gender} * 10.63) + ((\text{weight}/\text{height}^2) * 0.05) + 19.66$
Right Elbow Extension	$-(\text{age} * 0.08) + (\text{gender} * 8.33) + ((\text{weight}/\text{height}^2) * 0.16) + 12.37$

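### SAP 10.3 omits hip abductors from the predicted lower extremity composite but keeps them in the observed one, so LEC percent predicted, programmed as written, reads about 1.2 times too high

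*SAP*

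**What the plan says.** SAP 10.3 gives three formulas that bear on this point.

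- The observed LE composite is a sum of side-averaged strengths "for muscle group knee flexors, hip flexors, hip extensors, hip abductors and hip adductors": five groups.
- The predicted normal for the LE composite is a sum of side-averaged predicted values "for muscle group hip flexors, hip extensors, hip adductors and knee flexors": four groups.
- The percentage is then defined by "of predicted normal HHD values = (Observed strength value/ Predicted normal strength value) *100".

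For the upper extremity, the observed and predicted sums use the same list, "for muscle group gross grip, shoulder abductors, elbow flexors and elbow extensors".

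SAP 10.3.1 gives hip abduction equations for the dominant and non-dominant sides and says that baseline age and weight "will be used for the calculation of predicted values for shoulder abduction and hip abduction for all study time points".

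SAP 4.2 lists "Changes from baseline in UEC and LEC percent predicted based on reference equations adjusting for age, gender, height, and weight" among the tertiary endpoints for CL202 and CL301 subjects. Appendix 10.1 assigns it summary statistics, while SAP 8.6 names GEE for all continuous efficacy endpoints.

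Protocol 7.5.2.1.2 defines the score differently: "The mean of the five averages in percent predicted scores will be calculated to create a percent predicted LEC score", with hip abductors among the five. SAP section 1 says that where the two documents differ on analysis methods, "the SAP will take precedence over the protocol".

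**The concern.** If the numerator contains hip abductor strength and the denominator does not, the ratio is not a percentage of normal: a person of exactly normal strength in every group scores well above 100%. The excess depends on the predicted hip abductor share, which varies with sex, age and body size. It is therefore a different multiplier for each subject, and group means and SDs cannot be corrected afterwards with one constant.

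UEC percent predicted, named in the same endpoint, has no such inflation. Read side by side, the lower limbs would look better preserved relative to the upper limbs than they are.

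**Working it through.** The documents state no LEC percent predicted value, so there is no figure of the plan's own to reproduce. The size follows from the SAP 10.3.1 equations.

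**Inputs.** Equations for hip flexion, hip extension, knee flexion, hip adduction and hip abduction, as printed in SAP 10.3.1. Sides are averaged as in 10.3. Hip abduction is in Newtons and takes weight in Newtons; it is converted with 9.80665 N per kg. Age, weight and height are assumed, because the documents give no baseline distribution.

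**Formula.** As written, percent = 100 × observed(5) / predicted(4). With matching groups, percent = 100 × observed(5) / predicted(5). The observed value cancels, so for any non-zero composite

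factor = predicted(5) / predicted(4).

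**Man, 40 years, 75 kg, 1.75 m** (weight/height² = 24.49; weight = 735.5 N):

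- Hip abduction, non-dominant: 203.32 − 1.247×40 + 0.192×735.5 = 294.7 N
- Hip abduction, dominant: 195.24 − 1.184×40 + 0.198×735.5 = 293.5 N
- Mean: 294.1 N / 9.80665 = 29.99 kg

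| Predicted, kg | Man, 40 y, 75 kg, 1.75 m | Woman, 40 y, 62 kg, 1.62 m |
|---|---|---|
| Hip flexors | 55.65 | 36.19 |
| Hip extensors | 43.80 | 28.56 |
| Hip adductors | 31.87 | 21.55 |
| Knee flexors | 26.10 | 17.78 |
| **Four groups (SAP as written)** | **157.4** | **104.1** |
| Hip abductors | 29.99 | 20.53 |
| **Five groups** | **187.4** | **124.6** |
| Factor | 1.190 | 1.197 |
| A true 40% reads | 47.6% | 47.9% |
| A true fall from 40% to 35% reads | 5.95 points | 5.99 points |

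**Range.** Assumed grid: ages 20 to 70 in steps of 5 (11 values), BMI 17 to 35 in steps of 3 (7 values), four heights per sex (1.60–1.90 m for men, 1.50–1.75 m for women), so 11 × 7 × 4 × 2 = 616 profiles. The factor has minimum 1.157, median 1.200, mean 1.203, maximum 1.295, and 5th to 95th percentile 1.17 to 1.25. By sex it is 1.157–1.259 for men and 1.159–1.295 for women. The extremes depend on the grid; the centre near 1.2 does not depend on the example chosen.

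**Changes over time.** SAP 10.3.1 fixes the predictors at baseline, so each subject's denominator is constant across visits. A change in percentage points is multiplied by the same factor as the level; its sign and its size relative to baseline do not change.

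**Comparison with the protocol's definition.** The mean of five percentages weights groups equally, whereas a ratio of sums weights them by predicted strength. For the same man, under two assumed patterns of weakness:

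| Pattern | SAP as written | Ratio, five groups | Protocol mean of five |
|---|---|---|---|
| Hip flexors and extensors 60%, others 20% | 49.1% | 41.2% | 36.0% |
| Hip flexors and extensors 20%, others 60% | 46.2% | 38.8% | 44.0% |

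First row: observed = 0.6×(55.65+43.80) + 0.2×(31.87+26.10+29.99) = 77.26 kg, giving 77.26/157.4 and 77.26/187.4. The protocol mean is (60+60+20+20+20)/5 = 36.0. Restoring the missing term therefore does not by itself bring the SAP and the protocol into agreement.

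**The case against.** The strongest counter-argument is that the error may never reach the output. The SAP does not state in a single line that LEC percent predicted is the LE composite divided by its predicted normal; it gives a general rule for percentages. The protocol gives an explicit algorithm that includes hip abductors, and a programmer who follows it never touches the four-group sum. One can also argue that an incomplete list in a derivation appendix is not the kind of difference on analysis methods that the precedence clause was meant for.

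In part this stands: the bias arises only if 10.3 is programmed as written. But the predicted LE composite has no evident use in the SAP except as this denominator, and the SAP is the controlling document. A programmer who notices the gap must choose, without guidance, between two repairs that give different answers.

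The reach is also limited. The study is single-arm and open-label with safety as its primary endpoint. This efficacy endpoint is tertiary, and Appendix 10.1 plans summary statistics for it. That stands, and it caps the severity.

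The weakness patterns above are assumed, and they mainly illustrate the separate question of definition. They add nothing to the case for the missing term.

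Finally, the printed hip adduction slopes for women aged 55 or under (0.30 left, 0.00 right) look odd and were used as printed. With an assumed left slope of 0.03 instead, the woman's factor moves only from 1.197 to 1.201.

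**Conclusion.** The concern holds. SAP 10.3 compares a five-group observed composite with a four-group predicted one, and no other SAP text repairs this. Measured against the same ratio with all five groups in the denominator, any non-zero LEC percent predicted is overstated by a factor of about 1.2 (1.16 to 1.29 over the assumed profiles). A person of normal strength would score about 116% to 129%, and a true 5-point change would read about 6 points in the two worked examples. The range rests on assumed ages and body sizes; the existence of the error does not.

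The effect is confined to LEC percent predicted in CL202 and CL301 subjects. LEC in kg, UEC, the single-muscle percentages and the CL203 results are unaffected, and a composite of zero stays zero. It should be fixed before programming, but it does not threaten the primary or secondary analyses.

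**What to change.** In SAP 10.3, add hip abductors to the line that defines the predicted normal for the LE composite, so that it lists the same five groups as the observed composite.

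In the same edit, state which definition of LEC percent predicted applies: the ratio of the two sums, or the mean of the five per-muscle percentages in Protocol 7.5.2.1.2.

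The cost is one line of SAP wording for the missing group, a sentence for the definition, and one line of derivation code. No new data are needed.
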